# **PROTOCOL SYNOPSIS**

Study Title	The INFINITY TM Total Ankle Replacement Follow-up (ITAR)
Study Design	Prospective, multi-site, multi-year post-market clinical follow-up study
Study Group	Primary/Unilateral and/or bilateral Total Ankle Arthroplasty subjects implanted with INFINITY TM Total Ankle System
N Subjects	155 patients in 9 sites
Follow-Up Schedule	Subject enrollment will consist of a Pre-operative, Operative, 6 months, 1 yr., 2 yr., 5yr., 7 yr., 10 yr., and an unscheduled visit as needed.
Primary Objective	Evaluate the long-term survivorship of the INFINITY TM implant over 10 years
Secondary Objective(s)	
 
Secondary objectives assessed will be to:
 
Identify and assess the implant for component loosening and/or subsidence, any osteolysis and/or cyst formation through radiographic evaluation early and throughout the lifetime of the implant.
 
Compare the improvements in self-reported physical, mental, and social health measures from pre-op through 10 years post operatively; assessed by PROMIS® Global Health.
 
Compare pain and functional improvement in the Ankle Osteoarthritis Score (AOS), which is a visual analogue scale specifically designed as a modification of the Foot Function Index.
 
Compare the improvement in patient/physician reported function scores from pre-op through 10 years post-operatively, assessed by the FAOS questionnaire.
 
Compare satisfaction of total ankle replacement post operatively utilizing a four-point scale
 
Identify and report the safety of the implant in terms of complications and adverse events.
 

Inclusion Criteria	
 
Subjects to be included in the study must meet all of the following criteria:
 
Be 21 years of age or older at the time of surgery;
 
Diagnosed with unilateral and/or bilateral ankle joint disease;
 
Diagnosed with ankle joint damage from rheumatoid arthritis, post-traumatic, or degenerative arthritis;
 
Willing and able to consent to participate (written, informed consent;
 
Willing and able to attend the requested follow-up visits;
 
A clinical decision has been made to use INFINITYTM Total Ankle
 

Exclusion Criteria	
 
Subjects will be excluded from the study if they meet any of the following criteria:
 
Subjects with an ankle condition, as determined by the investigator, to be an inappropriate candidate for a total ankle replacement;
 

### **INTRODUCTION**

This statistical analysis plan is developed to guide the implementation of applicable statistical analysis and production of statistical output of US17-TAR-001 study. US-17-TAR-001 is prospective, multisite, multiyear post-market clinical study developed to evaluate the long-term survivorship of INFINITY® Total Ankle System implant over 10 years in the US. The study also seeks to assess the safety and possible complications with the implant and determine improvements in function and quality of life of patients. The study enrolled at least of 155 subjects.

The INFINITY® Total Ankle System is indicated in patients with ankle joints damaged by severe rheumatoid, post- traumatic, or degenerative arthritis, as well as for patients with a failed previous ankle surgery. Its intended use is to give patients limited mobility by reducing pain, restoring alignment and replacing the flexion and extension in the ankle joint.

The technological features of the INFINITY® Total Ankle System are similar to the predicate devices (INBONE® Total Ankle System, DePuy Agility™, INBONE® II Total Ankle System), which have all been cleared through the 510K process with the FDA, with regard to design and materials. The goal of the design was to limit the amount of bone resection and soft tissue dissection required for ankle arthroplasty; hence the overall profile of the INFINITY® Total Ankle System was significantly reduced along with the incision length required to perform the surgical procedure.

### **STUDY RATIONALE**

The primary outcome measure of this post-market clinical observational study is to assess the survivorship of INFINITYTM Total Ankle System at 10 years. The secondary outcome measures are to characterize the improvements after implantation over a 10-year period using patient reported outcome measures related to quality of life, pain and functional improvements, and safety of the implant.

### **STUDY OBJECTIVES**

This study aims to evaluate the long-term safety and survivorship of the INFINITY® implant over 10 years.

stryker

## Effectiveness objectives

The primary effectiveness objective is to evaluate the long-term survivorship of the INFINITY® implant and improvement in patient function and quality of life. Survivorship will be measured by the length of time until implant failure.

Improvement in subject function and quality of life was assessed using the PROMIS Global Health, Ankle Osteoarthritis Score (AOS) and FAOS Questionnaire.

In addition, the level of patient satisfaction of their total ankle replacement was assessed at each post-operative visit.

### Safety objectives

The safety objectives were to determine the long-term safety of the INFINITY® implant with respect to the patient experience of adverse events and complications associated with the implant such as component loosening and/or subsidence, any osteolysis and/or cyst formation through radiographic evaluation.

## Part numbers and brief descriptions of configurations

The INFINITY® configurations and sizes that were included in the study are listed in the table below. These products are manufactured according to ICH GCP in accordance with applicable Good Manufacturing Practice (GMP) and with the ISO 14155:2011: through relevant manufacturing and related validation processes.

Part No.	Description	Part No.	Description
	INFINITY ® Poly Insert	]	INFINITY® Tibial Component
33651106	POLY INSERT, SZ1/1+ 6MM	33650001	Tibial tray SZ1 STD
33651108	POLY INSERT, SZ1/1+	33650002	Tibial tray SZ2 STD
33651110	POLY INSERT, SZ1/1+	33650003	Tibial tray SZ3 STD
33651112	POLY INSERT, SZ1/1+	33650004	Tibial tray SZ4 STD
33652206	POLY INSERT, SZ2 6MM	33650005	Tibial tray SZ5 STD
33652208	POLY INSERT, SZ2 8MM	33650013	Tibial tray SZ3
Dago 6 of 22			04 October 2021

Table 1. List of **INFINITY**® and **INBONE**® configurations included in the study.

33652210	POLY INSERT, SZ2 10MM	33650014	Tibial tray SZ4
33652212	POLY INSERT, SZ2 12MM	33650015	Tibial tray SZ5
33653206	POLY INSERT, SZ2 +6MM		INFINITY® Talar Component
33653208	POLY INSERT, SZ2	33630021	Talar Dome SZ 1
33653210	POLY INSERT, SZ2	33630022	Talar Dome SZ 2
33653212	POLY INSERT, SZ2 +12MM	33630023	Talar Dome SZ 3
33653306	POLY INSERT, SZ3 6MM	33630024	Talar Dome SZ 4
33653308	POLY INSERT, SZ3 8MM	33630025	Talar Dome SZ 5
33653310	POLY INSERT, SZ3 10MM	INBON	NE® II Talar Component &
33653312	POLY INSERT, SZ3 12MM	220220901	Talar Dome SZ 1
33654307	POLY INSERT, SZ3 + 7MM	220220902	Talar Dome SZ 2
33654309	POLY INSERT, SZ3 + 9MM	220220903	Talar Dome SZ 3
33654311	POLY INSERT, SZ3 11MM	220220904	Talar Dome SZ 4
33654313	POLY INSERT, SZ3 13MM	220220905	Talar Dome SZ 5
33654406	POLY INSERT, SZ4 6MM	200347901	Talar Stem 10 mm
33654408	POLY INSERT, SZ4 8MM	200347902	Talar Stem 14 mm
33654410	POLY INSERT, SZ4 10MM		
33654412	POLY INSERT, SZ4 12MM		
33655407	POLY INSERT, SZ4 +7MM		
33655409	POLY INSERT, SZ4 +9MM		
33655411	POLY INSERT, SZ4 +11MM		
33655413	POLY INSERT, SZ4 +13MM		
33655506	POLY INSERT, SZ5 6MM		
33655508	POLY INSERT, SZ5 8MM		
33655510	POLY INSERT, SZ5 10MM		
33655512	POLY INSERT, SZ5 12MM		
33655512	POLY INSERT, SZ5 12MM		

### **STUDY DESIGN**

#### **Overview**

This study is a prospective, multi-site, multi-year post-market, follow-up clinical trial to evaluate the long-term survivorship of the INFINITY® Total Ankle System in the treatment of ankle joint damaged caused by severe rheumatoid, post- traumatic, or degenerative arthritis, as well as for patients with a failed previous ankle surgery. Prior to surgery, medical history, demographic, radiographic parameters and disease severity by COFAS type, varus/valgus deformity and function and quality of life of patients were collected.

At Day 0 (Surgery Day), information related to the subject's operation will be collected and recorded according to the Operative Information Case Report Forms, which included the following: Primary diagnosis, any previous surgery to index joint, date of operation, site location, surgical approach, instrumentation type (standard) or (additional approved INFINITY® instrumentation), concomitant operative procedures, cement use, intraoperative complications, and product description and eight-digit product code for all components implanted. Subjects were to return for clinical, functional and radiographic evaluations and safety evaluations at 6 months, 1 year, 2 years, 5 years, 7 years and 10 years post-surgery. The study planned to enroll 200 or more subjects in the US with 10 investigational sites, however, 155 patients participated when enrollment was closed. The study subjects included are those with ankle joints damaged by severe rheumatoid arthritis, post-traumatic disease, and degenerative arthritis and implanted with the INFINITY® Total Ankle System.

#### Inclusion/Exclusion Criteria

Subjects who met the following inclusion/exclusion criteria were voluntarily recruited by participating investigators:

#### **Inclusion Criteria:**

Subjects to be included in the study must meet all of the following criteria:

- Be 21 years of age or older at the time of surgery;
- Diagnosed with unilateral and/or bilateral ankle joint disease;
- Diagnosed with ankle joint damage from rheumatoid arthritis, post-traumatic, or

### stryker

degenerative arthritis;

- Willing and able to consent to participate (written, informed consent;
- Willing and able to attend the requested follow-up visits;
- A clinical decision has been made to use INFINITY™ Total Ankle System replacement prior to enrollment in the research.

## **Exclusion Criteria:**

Subjects will be excluded from the study if they meet any of the following criteria:

- Subjects with an ankle condition, as determined by the investigator, to be an inappropriate candidate for a total ankle replacement;
- Subjects requiring revision total ankle replacement of the ankle being considered for study.

### Table 2. Study schedule.

Procedures	Pre-op	Op.	6 mo +/-30 days	1 yr +/-60 days	2 yr +/-60 days	5 yr +/-60 days	7 yr +/-60 days	10 yr +/-60 days	Study Close
Informed Consent	Х								
Inclusion/Exclusion Criteria	Х								
Medical History & Demographics	Х								
Operative Surgical procedure/device		Х							
PROMIS Global Health	Х		Х	X	Х	Х	Х	Х	
Ankle Osteoarthritis Score (AOS)	Х		Х	Х	Х	Х	Х	X	
FAOS Questionnaire	Х		Х	Х	Х	Х	Х	Х	
Total Ankle Replacement			Х	Х	Х	Х	Х	Х	
Radiographic Assessment	Х		Х	Х	Х	Х	Х	Х	
Adverse Event Assessment		Х	Х	Х	Х	Х	Х	Х	
End of Study		 							Х
Surgical Intervention 									
*Sponsor-approved Unscheduled Visit 									

 $1\&^2$  These are not scheduled time point events but will be observed for throughout study participation.

### STATISTICAL METHODS

### **General Considerations**

All enrolled subjects who underwent total ankle replacement implanted with INFINITY™ or INBONE® product configurations listed in Table 1 will be included in the analysis. All data will be summarized for all subjects at baseline and at every post-surgery visit, namely at 6 months, 1, 2, 5, 7, and 10 year post surgery.

Categorical data will be displayed as frequency and percent, and continuous data will be displayed using descriptive statistics (N, mean, standard deviation, quartiles, minimum and maximum, CI). Subgroup analyses will be conducted for all the patient reported outcomes: PROMIS Global Health AOS and FAOS. Subgroup analysis and comparisons will be presented for the following factors:

- surgical instrumentation type (standard vs additional approved instrumentation),
- type of primary disease diagnosis (Rheumatoid arthritis, Post traumatic, Degenerative);
- COFAS type (Types 1-4);
- Varus and/or valgus degree of deformity
- Radiographic radiolucency.

Radiolucency factors will be categorized independently with respect to linear and cystic radiolucency as follows:

Linear radiolucency:	Group 1: Present Linear radiolucency (>2mm)
	Group 2: Absent Linear radiolucency (>2mm)
Cystic radiolucency:	Group 1: Present Cystic radiolucency (>5mm)
	Group 2: Absent Cystic radiolucency (>5mm)

Subgroup analysis of the patient satisfaction of their total ankle replacement post operatively will only be done for surgical instrumentation type.

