## Surgeon-completed Radiographic Report

This report includes usual standard of care pre-operative radiographs will include a standing AP and lateral film of

the ankle. Arthritis can be assessed by CT if available but, not required for this study.

Coronal plane deformity should be measured in degrees as the angle between a line perpendicular to the anatomical axis of the tibia and a line drawn along the top of the talar dome see (see figure) and recorded as either varus or valgus.

The Canadian Orthopaedic Foot and Ankle Society (COFAS) end-stage arthritis classification should be identified and recorded as:

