### **Group Comparisons**

At each post-surgery visit, the patient reported outcome (PROMIS, AOS and FAOS) score and the change from baseline scores will be analyzed. Analysis of covariance (ANCOVA) with baseline score as a covariate factor will be implemented for all comparisons (i.e., comparison by disease diagnosis). The components of the ANCOVA model are: baseline scores, subgroups or independent factor and subgroup-by-baseline interaction.

Adjusted mean of subgroups with 95% confidence intervals will be presented. Bonferroni pairwise adjusted comparison of means will be done when significant differences among the group is established.

All statistical analysis tables for PROMIS, AOS and FAOS will be will have the elements as presented in the template below.

Visit	Factor (or sub-factor X)	All Subjects (N=xx)	Group 1 (N=xx)	Group 2 (N=xx)
Pre-operative	N	XX	XX	XX
-	Mean $\pm$ SD	$xx.x \pm xx.x$	$xx.x \pm xx.x$	$xx.x \pm xx.x$
	1st Q, Median, 3rd Q	XX.X, XX.X, XX.X	XX.X, XX.X, XX.X	XX.X, XX.X, XX.X
	Min, Max	XX.X , XX.X	XX.X , XX.X	XX.X , XX.X
	Difference in means			XX.X
	p-value for mean difference*=0			X.XXX
Post-op Visit	Ν	XX	XX	XX
-	Mean $\pm$ SD	$xx.x \pm xx.x$	$xx.x \pm xx.x$	$xx.x \pm xx.x$
	1st Q, Median, 3rd Q	xx.x, xx.x, xx.x	XX.X, XX.X, XX.X	xx.x, xx.x, xx.x
	Min, Max	XX.X , XX.X	XX.X , XX.X	XX.X, XX.X
	p-value for change from baseline***	X.XXX	X.XXX	X.XXX
	Difference in group means			XX.X
	p-value for group difference**=0			X.XXX
	Adjusted mean $\pm$ se**		$xx.x \pm xx.x$	$xx.x \pm xx.x$
	95% CI for the Difference in Mean**			(xx.x , xx.x)
	Change from Baseline			
	N	XX	XX	XX
	Mean $\pm$ SD	$xx.x \pm xx.x$	$xx.x \pm xx.x$	$xx.x \pm xx.x$
	1st Q, Median, 3rd Q	xx.x, xx.x, xx.x	xx.x, xx.x, xx.x	xx.x, xx.x, xx.x
	Min, Max	XX.X , XX.X	XX.X , XX.X	XX.X, XX.X
	Difference in group means			XX.X
	Adjusted mean ± se**		$xx.x \pm xx.x$	$xx.x \pm xx.x$
	95% CI for the Difference in Mean**			(xx.x , xx.x)
	p-value for group mean difference=0**			X.XXX

Table 3	. Template	of statistical	tables for	PROMIS,	AOS and FAOS
---------	------------	----------------	------------	---------	--------------

Note: Results will be presented for each post-operative visit.

\*One-way analysis of variance for group difference. \*\*Results of ANCOVA, group variable as fixed effect and baseline as covariate, means adjusted for baseline.

\*\*\*t-test or Wilcoxon test p-value for two related samples.

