## LISTING OF TABLES

Table	1.1	Subject Disposition
Table	1.2	All Protocol Deviations
Table	1.3	Demographics and Clinical Characteristics
Table	1.4	Medical History
Table	1.7	Surgical and Operative Information
Table	1.8	Additional Surgical Procedures Performed
Table	2.1	Life-table survivorship of INFINITY® Total Ankle System
Table	2.2.1	Ankle Osteoarthritis Score (AOS) by Instrumentation Type
Table	2.2.2	Ankle Osteoarthritis Score (AOS) Comparison by COFAS
Table	2.2.3	Ankle Osteoarthritis Score (AOS) by Disease Diagnosis
Table	2.2.4	Ankle Osteoarthritis Score (AOS) by Study Site
Table	2.2.5	Ankle Osteoarthritis Score (AOS) Comparison of Degenerative & Post-
Table	2.2.6	traumatic vs Inflammatory (RA) Ankle Osteoarthritis Score (AOS) Comparison by Degree of Valgus/Varus
		deformity
Table	2.2.7	Ankle Osteoarthritis Score (AOS) Comparison by Linear radiolucency
		(>2mm)
Table	2.2.8	Ankle Osteoarthritis Score (AOS) Comparison by Cystic Radiolucency
Table	2.3.1	(>5mm) PROMIS Global Health Score by Instrumentation Type
Table	2.3.2	PROMIS Global Health Score Comparison by COFAS
Table	2.3.3	PROMIS Global Health Score by Disease Diagnosis
Table	2.3.4	PROMIS Global Health Score by Study Site
Table	2.3.5	PROMIS Global Health Score Comparison of Degenerative & Post-traumatic
		vs Inflammatory (RA)
Table	2.3.6	PROMIS Global Health Score Comparison by Degree of Valgus/Varus
		deformity
Table	2.3.7	PROMIS Global Health Score Comparison by Linear radiolucency (>2mm)
Table	2.3.8	PROMIS Global Health Score Comparison by Cystic Radiolucency (>5mm)
Table	2.4.1	Foot and Ankle Outcome Score by Instrumentation Type
Table	2.4.2	Foot and Ankle Outcome Score Comparison by COFAS

Table	2.4.3	Foot and Ankle Outcome Score by Disease Diagnosis
Table	2.4.4	Foot and Ankle Outcome Score by Study Site
Table	2.4.5	Foot and Ankle Outcome Score Comparison of Degenerative & Post-
		traumatic vs Inflammatory (RA)
Table	2.4.6	Foot and Ankle Outcome Score Comparison by Degree of Valgus/Varus
		deformity
Table	2.4.7	Foot and Ankle Outcome Score Comparison by Linear radiolucency (>2mm)
Table	2.4.8	Foot and Ankle Outcome Score Comparison by Cystic Radiolucency
		(>5mm)
Table	2.5.1	Patient TAR satisfaction by visit and Instrumentation Type
Table	3.1	Radiographic Assessment by Visit
Table	3.2	Surgical Intervention by Visit
Table	4.1	Summary of Adverse Events – Treated Population
Table	4.2	Treatment Emergent Adverse Events
Table	4.3	Treatment Emergent Adverse events by visit

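### Coronal deformity is recorded in degrees, but the SAP treats it as a subgroup factor with no groups or cut-point; a prespecified continuous term would use the data better and leave no cut to choose

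*SAP*

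**What the plan says.** **How the angle is collected.** Protocol, Surgeon-completed Radiographic Report: "Coronal plane deformity should be measured in degrees as the angle between a line perpendicular to the anatomical axis of the tibia". The result is recorded as varus or valgus, so the database holds a size in degrees and a direction.

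**How the SAP uses it.** General Considerations introduces a list with "Subgroup analysis and comparisons will be presented for the following factors", and one entry is "Varus and/or valgus degree of deformity". The instrumentation, diagnosis and COFAS entries name their categories. Radiolucency gets its own paragraph ("Radiolucency factors will be categorized independently with respect to linear and cystic radiolucency as follows"), with thresholds of 2 mm and 5 mm. The deformity entry has no groups, no cut-point and no rule for combining varus with valgus.

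**How the factors are modelled.** Group Comparisons: "The components of the ANCOVA model are: baseline scores, subgroups or independent factor and subgroup-by-baseline interaction". The footnote to Table 3 reads "Results of ANCOVA, group variable as fixed effect and baseline as covariate, means adjusted for baseline", and the template columns are Group 1 and Group 2. The template is meant to be general: the sentence introducing it begins "All statistical analysis tables for PROMIS, AOS and FAOS will be". Bonferroni pairwise comparisons follow a significant group effect.

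**What will be produced.** The Listing of Tables includes Table 2.2.6, "Ankle Osteoarthritis Score (AOS) Comparison by Degree of Valgus/Varus" deformity, with matching Tables 2.3.6 (PROMIS) and 2.4.6 (FAOS). None of these titles gives a cut, whereas the radiolucency titles give theirs.

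**The concern.** Grouping a measured angle costs two things.

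1. **Information.** Patients on the same side of a cut are treated as identical, and those just either side of it as different in kind. If the effect of deformity on the scores is graded, a grouped analysis is less likely to find it.
2. **Prespecification.** With no groups stated, someone has to choose them. The SAP is dated 04 October 2021 and reports enrolment as already closed at 155, so pre-operative angles and early post-operative scores could be available when the choice is made. Outcome analyses are also planned at each post-surgery visit. A cut chosen because it separates the scores well would make the nominal p-value too small.

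At stake is the interpretation of three planned tables, each repeated at six post-operative visits. The primary endpoint is not involved.

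**Working it through.** The plan gives no power, alpha or effect size for this comparison, and the protocol states that the sample size was not calculated statistically. There is therefore no figure of the plan's own to reproduce.

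**Inputs**
- From the SAP: N = 155. This is an upper limit, because patients with missing data are excluded.
- Assumed: two-sided alpha 0.05 (in line with the SAP's 95% intervals); absolute angle = |normal with SD 9 degrees|; residual score SD 20; linear effect of 0.83 points per degree. The documents give none of these.

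**Step 1: implied correlation.** The SD of the absolute angle is 9 × √(1 − 2/π) = 5.43 degrees, and its mean is 9 × √(2/π) = 7.18. The slope contributes 0.83 × 5.43 = 4.50 points, so r = 4.50 / √(4.50² + 20²) = 0.220.

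**Step 2: power with the angle continuous** (Fisher z). Power = Φ(atanh(0.220) × √(155 − 3) − 1.96) = Φ(2.75 − 1.96) = Φ(0.79), about 78-79%. Simulation gives 78%.

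**Step 3: power with two groups.** With a share p above cut c, the fraction of linear information kept is [E(x; x>c) − p·E(x)]² / [p(1 − p)·Var(x)], where E(x; x>c) = 18·φ(c/9) and Var(x) = 29.4.
- Median split: (5.72 − 3.59)² / (0.25 × 29.4) = 0.62 kept. Power is Φ(atanh(0.220 × √0.62) × √152 − 1.96), about 57%.
- Cut at 10 degrees (p = 0.267): (3.87 − 1.91)² / (0.1955 × 29.4) = 0.67 kept. Power is about 61%.
- Simulations of these two cuts fall between 57% and 62%.

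**Step 4: three equal groups.** More groups keep more information: 79% for three equal groups of a normal angle and 86% for four, when the order of the groups is used. The SAP's group effect is unordered, however, so three groups are tested on 2 degrees of freedom. Simulated power is about 57%, no better than a median split.

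**Step 5: a cut chosen after seeing the scores.** With no true association, taking the smallest p-value over cuts at 5, 8, 10, 12 and 15 degrees rejects in about 17% of simulated trials, against 5% for one fixed cut. Two candidate cuts give about 9% and three about 12%. These rates are for one score at one visit.

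**Step 6: sensitivity.**

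| Absolute angle | Slope (points/degree) | Continuous | Median split | Cut at 10 degrees |
|---|---|---|---|---|
| \|normal, SD 9\| | 0.83 | 78% | 57% | 61% |
| Exponential, mean 7 | 0.62 | 75% | 46% | 58% |
| Exponential, mean 7 | 0.83 | about 94% | about 69% | about 81% |

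The absolute levels move with the assumptions. The ordering does not.

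**The case against.** **The SAP never says the angle is cut.** This is correct. The model sentence allows an independent factor as well as subgroups, which could admit a continuous term. The two-column template also serves COFAS type (four categories) and diagnosis (three), so it does not fix two groups. A reader might infer that the angle will be dichotomised, and the documents do not support that. They do support grouping as the intended form, through the subgroup heading, the group fixed effect, the adjusted subgroup means and the pairwise comparisons. Moving to three groups does not recover the power (step 4).

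**A threshold already exists.** More than 10 degrees appears in the COFAS Type 2 definition in both documents, and a protocol footnote ties it to this same coronal angle. It is the natural default. But the SAP does not assign it to this factor, and COFAS type is a separate factor that partly captures the same deformity. Even as a fixed cut, it gives about 61% power against 78%.

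**The 17% depends on a search.** This also stands. A reader might infer that a favourable cut was or will be selected, or that the planned tables carry a 17% error rate. The documents show only that no rule prevents a search.

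**It is one subgroup display in a single-group observational study.** True. Whether deformity modifies benefit is not a stated objective, and no hypothesis is powered. That limits the weight of the point. Still, p-values are planned for these tables, and the better method uses data already collected.

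**Conclusion.** The point holds as a secondary matter that should be corrected. A quantity collected in degrees is assigned to a categorical analysis whose groups are undefined, and the SAP postdates the close of enrolment. Under the stated assumptions, grouping lowers power from about 78% to about 57-62% with two groups and about 57% with three. A cut picked from five after seeing the scores would raise type I error to about 17%; this is a conditional risk, not a finding about what was done.

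The power figures rest on an assumed angle distribution, a linear effect, a residual SD of 20, and all 155 patients contributing. If the true relation were a step at a known angle, a cut at that angle would lose little, but the documents do not claim one. Survivorship, the primary endpoint, is unaffected.

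**What to change.** Amend SAP General Considerations and Group Comparisons along these lines:

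- For Tables 2.2.6, 2.3.6 and 2.4.6, deformity enters the ANCOVA as absolute degrees (continuous), with baseline score and direction as main effects. Direction is varus or valgus, with 0 degrees handled as neutral.
- The stated comparison is the 1-degree-of-freedom test of degrees, reported per 5 degrees with a 95% confidence interval. Simulated power under the inputs above is about 78%.
- The degrees-by-direction interaction and the linearity of the effect (spline or residual plot) are secondary checks.
- Any grouped display uses the documents' existing threshold of more than 10 degrees and is descriptive only.

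The interaction should stay out of the main test. With an even varus/valgus split (an assumption), a direction-specific slope has only about 50% power and a joint 2-degree-of-freedom test about 69%, so including it would give back much of the gain.

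**Cost.** SAP wording and a modified table shell for three tables; no new data. The downside is that the main test assumes a linear effect and one slope common to varus and valgus, which the secondary checks are there to examine.
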